| IBA | Independent Blinded Assessor |
| LLDAS | Lupus Low Disease Activity State |
| MedDRA | Medical Dictionary for Regulatory Activities |
| NR | Non-Responder |
| PI | Principal Investigator |
| R | Responder |
| RAP | Reporting and Analysis Plan |
| SLEDAI-2K | Systemic Lupus Erythematosus Disease Activity Index 2000 |

Trademarks

| Trademarks owned by GlaxoSmithKline group of companies |
|---|
| None |

| Trademarks not owned by GlaxoSmithKline group of companies |
|---|
| None |

1. INTRODUCTION

This RAP addendum is supplemental to the RAP (Dated: 05/AUG/2020), and based on protocol amendment 04 (Dated: 30/APR/2020) of study 205646.

The purpose of this RAP addendum is to document minor additions/clarifications made after RAP approval but prior to Database Release.

2. CHANGES/CLARIFICATIONS TO THE RAP

2.1. Additional Cochran-Mantel-Haenszel (CMH) analysis (RAP Section 7)

The RAP specifies that CMH analysis will be conducted for

- Disease Control at Week 52: RAP Section 7.1.5.1
- Clinical Remission at Week 64: RAP Section 7.2.5.1
- Disease Control at Week 104: RAP Section 7.3.5.1

Following re-review of the FDA Request 29 June 2020 – comment 5:

To facilitate an evaluation of benefit-risk, report point estimates and 95% CI for the difference in proportions for these endpoints

It was decided that most other binary endpoints would also conduct the CMH analysis. The exceptions are the following outputs:

- Disease control at Week 52 by subgroup
- Sensitivity analyses that were unadjusted for covariates (disease control and clinical remission)
- COVID-19 additional analyses using multiple imputation methods (disease control and clinical remission)

2.2. Systemic Lupus Erythematosus Disease Activity Index (SLEDAI)-2K Missing Item Scores (RAP Section 15.6.3, Section 15.6.4, Section 15.6.5, Section 15.6.6 and Section 15.6.9)

The RAP Section 15.6.3 states the following:

“SLEDAI-2K missing scores for laboratory parameters i.e.

CCI - This section contained Clinical Outcome Assessment data collection questionnaires or indices, which are protected by third party copyright laws and therefore have been excluded.

CCI - This section contained Clinical Outcome Assessment data collection questionnaires or indices, which are protected by third party copyright laws and therefore have been excluded.

Will be imputed from the previous assessment if the previous assessment is no more than 35 days prior.”

For clarification, the following rules apply for SLEDAI-2K missing item scores:

- It is only the 8 lab items that can be imputed. If any of the other 16 items are missing, they will be left missing.
- An imputed assessment cannot be used to impute another assessment.
- The imputation of these missing lab items is carried out independently for the Principal Investigator (PI) and Independent Blinded Assessor (IBA), i.e. the PI assessment of the lab items will never be carried forward to a missing IBA assessment and vice versa.

The following sections of the RAP should not re-define what happens with missing SLEDAI-2K item scores, they should all use the principles stated above:

- RAP Section 15.6.4: Disease Control
- RAP Section 15.6.5: Clinical Remission
- RAP Section 15.6.6: Complete Remission
- RAP Section 15.6.9: Lupus Low Disease Activity State (LLDAS)

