In the existing table, there was one row for subjects who complete at Week 52 after the COVID environment onset date. To cover the scenario of missing (or partial non-informative) SLEDAI-2K data, that row has been split into two rows, as shown in [Table 1](#) below:

Table 1 Graphical Representation of the Additional Analyses

| COVID-19 environment Onset date | | Description | Primary Analysis Hybrid | COVID Attributed | COVID Environment | Pre- COVID |
|------------------------------------|--------------|--|-------------------------------|---------------------|----------------------|---------------|
| X | _____0 Comp. | Subject Completes Week 52 on or after COVID-19 environment onset date and has a completed (or partial but informative) S2K Score | R/NR | R/NR | Imputed | Excluded |
| X | _____0 Comp. | Subject Completes Week 52 on or after COVID-19 environment onset date and has a missing or partial non-informative S2K Score that cannot be determined to definitely be either R or NR | NR | Imputed | Imputed | Excluded |

Comp. = Completed; R/NR = Responder/Non-Responder based on SLEDAI-2K criteria; NR = Non-Responder

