7. EFFICACY ANALYSES

The primary objective of the study is to demonstrate superiority (improvement in response rate) of co-administration of belimumab plus rituximab (Arm B: Combination) over belimumab monotherapy (Arm A: Control), when comparing the primary efficacy endpoint at Week 52 in subjects with SLE.

An exploratory summary of Arm B (Combination) vs Arm C (Reference) will also be shown.

SLEDAI-2K score has been measured by both the principal investigator (PI) and the independent blinded assessor (IBA). The key differences between these assessments is the frequency of assessment and awareness of the treatment allocation for Arm C:

- The principal investigator conducts a SLEDAI-2K assessment every 4 weeks in Year 1 (at least every 8 weeks in Year 2), whereas the independent blinded assessor conducts a SLEDAI-2K assessment at a reduced set of key time points (weeks baseline, 12, 26, 40, 52, 64, 80, and 104).
- The principal investigator knows which of their subjects are randomised to treatment arm C, but does not know if their remaining subjects are randomised to arm A or arm B. The independent blinded assessor however is not aware of any MITT population subject's treatment randomisation (Section 4).

Due to the level of blinding the primary and major secondary efficacy endpoints will be conducted using the independent blinded assessors' SLEDAI-2K assessment. Note however the PI assessment of SLEDAI-2K at baseline, is used as the baseline covariate in all adjusted analysis (the baseline SLEDAI-2K assessment is conducted prior to randomisation).

The other secondary endpoints analysis utilises the greater visit frequency of the principal investigator assessment. This is particularly pertinent for differentiating between treatments when considering time to response or duration of response. In by visit summaries, it also allows for the assessment of fluctuating response.

The primary and major secondary efficacy endpoints are repeated using the principal investigator assessment.

Details of the planned displays are provided in Section 15.11 and are based on GSK data standards and statistical principles. Listings of all key efficacy endpoints will be provided [L12.01 – L12.02, and L22.01-L22.02].

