Assessments after IP discontinuation and assessments after Treatment Failure will be included. Subjects who withdraw from the study will be non-responders.

The impact of the different IP discontinuation components of the endpoint for the Hybrid and composite estimands is summarised by considering 6 hypothetical scenarios:

Table 2 Scenarios for the components of the Hybrid and composite endpoint

| Example Subject | SLEDAI-2K score at Week 52 | Study Withdrawal(including Lost to Follow-up, or Death) prior to Week 52 | Treatment Failure prior to Week 52 | IP Discontinuation prior to Week 52 | Main Estimand Hybrid | Supplemental Estimand Composite |
|-----------------|--|--|------------------------------------|-------------------------------------|----------------------|---------------------------------|
| 1 | >2 | N | N or Y | N or Y | NR | NR |
| 2 | <=2 | N | N | N | R | R |
| 3 | <=2 | N | N | Y | R | NR |
| 4 | <=2 | N | Y | N or Y | NR | NR |
| 5 | Incomplete* or entirely missing | N | N or Y | N or Y | NR | NR |
| 6 | Missing - does not exist due to study withdrawal | Y | N or Y | Y | NR | NR |

R = Responder; NR = Non-Responder

*Incomplete: does not include partial scores where it is possible to determine that the total score must be >2, or that the maximum possible score (assuming worst case for missing data) is <=2 (see Section 15.6.4 Partial but informative SLEDAI-2K score).

A full breakdown of scenarios ‘by subject type’ and including Hybrid On Treatment and Treatment Policy is provided in Section 15.6.4

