15.6.4. Disease Control

| |
|---|
| Endpoint Definition |
| The disease control endpoint is defined as: 
 • SLEDAI-2K score ≤ 2 (IBA*), |

| |
|---|
| 
 • Not a Treatment failure • Not a Study withdrawal 
The same derivation will be applied to the secondary endpoint “Disease control (PI)” using the principal investigators assessment of the SLEDAI-2K.
 |
| 
Imputation of Missing values – IBA assessment
 |
| 
Missing IBA assessments based on laboratory assessments i.e.: Urinary Casts, Hematuria, Proteinuria, Pyuria, Low Complement, Increased DNA Binding, Thrombocytopenia, and Leukopenia will be imputed from the PI assessment if the laboratory sample (for the PI assessment) was drawn no more than 35 days prior. An imputed assessment can not be used to impute another assessment. There will be no imputation of missing IBA assessments based on physical examination
 |
| 
Imputation of Missing values – PI assessment
 |
| 
If an individual question of the SLEDAI-2K assessment or the full assessment is missed the previous assessment may be used as a substitute if it was no more than 35 days prior. An imputed assessment cannot be used to impute another assessment.
 |
| 
Partial but informative SLEDAI-2K score
 |
| 
If after imputation for missing questions the SLEDAI-2K total score is still not derivable due to missing individual questions, then the minimum possible score will be considered. If the minimum possible score is >2 then the subject will be considered as a non-responder. Similarly a maximum possible score will be considered to determine if the maximum possible score is ≤2.
 |
| 
Time to Disease Control Sustained to Week 104
 |

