15.6.5. Clinical Remission

| |
|--|
| 
Endpoint Definition
 
Clinical remission for Arms A & B (secondary endpoint) is defined as:
 
 • Clinical SLEDAI-2K score[#] = 0 (IBA*), • Not a Treatment Failure • Did not withdraw from the study • 7-day average corticosteroids at a prednisone equivalent dose of 0mg/day for the assessment (7 day average is the average of current and 6 previous days) 
[#]See Section 15.6.3
 
*at baseline the principal investigators assessment will be used
 
The same derivation will be applied to the secondary endpoint “clinical remission (PI)” using the principal investigators assessment of the SLEDAI-2K.
 |
| 
Imputation of Missing values – IBA assessment
 
Missing IBA assessments based on laboratory assessments i.e.: Urinary Casts, Hematuria, Proteinuria, Pyuria, Thrombocytopenia, and Leukopenia will be imputed from the PI assessment if the laboratory sample (for the PI assessment) was drawn no more than 35 days prior. An imputed assessment can not be used to impute another assessment.
 
There will be no imputation of missing IBA assessments based on physical examination
 |
| 
Imputation of Missing values – PI assessment
 
If an individual question of the SLEDAI-2K assessment or the full assessment is missed the previous assessment may be used as a substitute if it was no more than 35 days prior. An imputed assessment cannot be used to impute another assessment.
 |
| 
Partial but informative Clinical SLEDAI-2K score
 
If after imputation for missing questions the Clinical SLEDAI-2K score is still not derivable due to missing individual questions, then the minimum possible score will be considered (sum of the answered questions). If the minimum possible score is >0 then the subject will be considered as an observed non-responder (rather than non-responder due to missing data).
 |

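### Does RAP Addendum 1 leave a blank laboratory item on the blinded assessor's SLEDAI-2K with no usable fill, so that responders are lost?

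*SAP*

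**What the plan says.** The primary endpoint (disease control at Week 52) and both major secondary endpoints (clinical remission at Week 64, disease control at Week 104) use the IBA's SLEDAI-2K. RAP Section 7 places the IBA assessments "at a reduced set of key time points (weeks baseline, 12, 26, 40, 52, 64, 80, and 104").

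For a blank IBA laboratory item, RAP Section 15.6.4 said that it "will be imputed from the PI assessment if the laboratory sample (for the PI assessment) was drawn no more than 35 days prior". Section 15.6.5 has the same rule for the six laboratory items that count towards clinical remission: "Urinary Casts, Hematuria, Proteinuria, Pyuria, Thrombocytopenia, and Leukopenia".

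Addendum 1, Section 2.2, replaces these rules. It restates the general rule of RAP Section 15.6.3 for the laboratory items ("Will be imputed from the previous assessment if the previous assessment is no more than 35 days prior"), applies it to the IBA and PI independently ("the PI assessment of the lab items will never be carried forward to a missing IBA assessment and vice versa"), and says that Sections 15.6.4, 15.6.5, 15.6.6 and 15.6.9 must not redefine it. The addendum describes itself as recording "minor additions/clarifications made after RAP approval but prior to Database Release".

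In RAP Section 7.1.4, Table 2, an incomplete score is a non-response in the main estimand. The footnote limits this: incomplete "does not include partial scores where it is possible to determine that the total score must be >2", or where even the worst case for the blanks is at most 2. Addendum 1, Section 2.5, deals with a subject who completes Week 52 on or after the COVID-19 onset date and "has a missing or partial non-informative S2K Score that cannot be determined to definitely be either R or NR". That subject is a non-responder in the primary analysis, but the response is imputed in the COVID Attributed and COVID Environment analyses.

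**The concern.** With the PI route closed, a blank IBA laboratory item can be filled only from an earlier IBA assessment, and those are months apart. Yet complement, anti-dsDNA, urinalysis and blood counts are scheduled at Weeks 52, 64 and 104, and RAP Section 15.6.3 ties a sample taken from 10 days before to 7 days after to each assessment. No stated step uses that sample to score an item the assessor left blank.

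A subject with all 16 clinical items scored and the laboratory result on file could therefore be counted a non-responder because a field was empty. That would cost responders and a little power, and would bias the comparison if blanks were more common in one arm.

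**Working it through.** **1. Reach of the carry-forward.** Inputs: the IBA weeks in RAP Section 7; windows of ±7 days, or ±28 days for COVID-19 reasons (protocol Section 2, Tables 1 and 2, footnote a); the 35-day limit. Minimum gap = 7 × (difference in weeks) − 2 × window.

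| Target visit | Previous IBA visit | Nominal gap | Minimum, ±7 | Minimum, ±28 |
|---|---|---|---|---|
| Week 52 | Week 40 | 84 d | 84 − 14 = 70 d | 84 − 56 = 28 d |
| Week 64 | Week 52 | 84 d | 70 d | 28 d |
| Week 104 | Week 80 | 168 d | 154 d | 112 d |

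In normal windows the gap is at least twice the limit. The fill works only after an unscheduled IBA assessment or, at Weeks 52 and 64, if the two visits move at least 84 − 35 = 49 days closer together. From the scheduled visits it can never work at Week 104.

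**2. Which blanks change the outcome.**
- *Disease control.* The maximum score is 105 for 24 items and 101 for the 22 non-serological items (RAP Section 15.6.3), so the two serology items carry 105 − 101 = 4 points. If both are blank and the rest are 0, the possible score runs from 0 to 4. It straddles the cut-off of 2, and the subject is a non-responder. If the answered items already exceed 2, the blank makes no difference.
- *Clinical remission.* The score must be 0, so a blank among the six laboratory items on an otherwise zero score cannot be resolved. Serology is not in this score.

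**3. What keeps blanks rare.** The assessor must hold a source document describing the laboratory findings behind the score (protocol Table 1, footnote t). Local results are required when central ones are late for response evaluation (protocol Appendix 9). The sample window runs to day +7. The database is cleaned before release (RAP Section 3.2).

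**4. Checks already planned.** Addendum 1, Section 2.3, extends both tipping-point analyses to missing or undetermined partial scores, whether or not the subject withdrew. They run at Week 52 if 0.001 < p ≤ 0.05 (RAP Section 7.1.6). The two COVID analyses impute post-onset cases at Week 52. PI-based repeats are planned (RAP Section 7; Addendum 2 tables 22.08 and 22.19).

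**5. Size.** First, the plan's own power (protocol Section 10.2: 10% vs 35%, 70 vs 140, two-sided 5%), by a pooled two-proportion z-test:
- Pooled rate = (7 + 49)/210 = 0.2667. SE under the null = √[0.2667 × 0.7333 × (1/70 + 1/140)] = 0.0647. SE under the alternative = √[0.09/70 + 0.2275/140] = 0.0540.
- Power = Φ[(0.25 − 1.96 × 0.0647)/0.0540] = Φ(2.28) = 98.9%, against a stated figure of at least 98%. For 10% vs 25% it gives 75.4%, against 75% in Table 5.

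Let m be the share of would-be responders coded non-responders for this reason. The documents give no value, so m is assumed, with both rates multiplied by (1 − m):

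| m | Difference (10% vs 35%) | Power, 10% vs 35% | Power, 10% vs 25% | Power, 10% vs 35%, only Arm B affected |
|---|---|---|---|---|
| 0 | 25.0 points | 98.9% | 75.4% | 98.9% |
| 2% | 24.5 | 98.7% | 74.3% | 98.5% |
| 5% | 23.75 | 98.3% | 72.5% | 97.8% |
| 10% | 22.5 | 97.5% | 69.3% | 95.8% |

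At m = 5% the expected loss is 0.05 × 7 = 0.35 responders in Arm A and 0.05 × 49 = 2.45 in Arm B. At the design rates, power reaches 90% only at m = 31.6% in both arms, or 18.0% if Arm B alone is affected. The documents give no Week 64 response rates, so no power figure is offered there.

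**The case for a change.** The case for acting is that the data already exist and none of the planned checks isolates the problem. The tipping-point analyses vary an assumed response probability and are conditional on the p-value. The COVID analyses impute response status, not the item, and only after onset; their Week 64 and Week 104 versions are not in Addendum 2's abridged list. The PI repeats replace all 24 items, not just the blank one. A supportive analysis scoring blank items from the visit's own sample, with a count by arm, would be cheap and would take nothing from the PI. The sponsor also wrote and revised a rule for blanks, so it expected some.

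These facts stand, but they support an optional extra and do not show an error. Scoring from the sample needs a list of items that require no judgement. Proteinuria is read as the investigator evaluates it, and the item definitions are withheld in this copy. At Week 64, where a blank matters most, serology is outside the score, so few cases might be resolved. Any such analysis would follow the Week 52 unblinding and could not alter a confirmatory conclusion. Some separation is also already planned: Section 15.6.5 distinguishes observed non-response from non-response due to missing data, and Addendum 2 adds first-reason tables (22.04 and 22.15). Their row layouts are in shells not available here, so the plan cannot be faulted for lacking a particular row.

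**Conclusion.** The gap is real but narrow, and it results from a fair trade-off. Keeping the PI's scores out of the IBA's record protects the assessment on which the confirmatory endpoints rest. The price is that an undetermined IBA score counts as non-response, which is how the main estimand treats other missing outcomes. Arms A and B are blinded to each other and share the rule, so bias would need blanks to differ by arm, and nothing in the documents suggests that.

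At the design rates, losing 2% to 10% of would-be responders in both arms costs 0.5 to 2.5 points of difference and at most 1.4 points of power; in the 10% vs 25% scenario it costs 1.1 to 6.1 points of power. These sizes rest on assumed values of m and on a z-test standing in for the planned logistic regression. Analysts who wish to can count by arm, within tables 22.04 and 22.15, the subjects who were non-responders only because of blank IBA laboratory items. That needs no amendment, and the results are sound without it.

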2.3. Tipping Point Analysis (RAP Section 7.1.6)

The RAP Section 7.1.6 describes the tipping point analyses only in terms of “missing data caused by study withdrawal”. This description is clarified here to also include any missing/partial non-informative SLEDAI-2K data, regardless of study withdrawal.

To explicitly clarify this in terms of the two strategies, the bold text has been added to the following existing RAP text:

“The first tipping point analysis will use the Hybrid strategy (as described in RAP Section 7.1.4 as per the primary estimand). If a subject’s study withdrawal (**or missing data**) is subsequent to treatment failure the subject will still be considered as a non-responder, i.e. the non-responder assumption will only be varied for withdrawn subjects (**or subjects with missing/partial non-informative SLEDAI-2K data**) that were not treatment failures.

The second tipping point analysis will use the treatment policy strategy (RAP Section 7.1.4). In this approach, treatment failure data is ignored, i.e. the non-responder

assumption is varied for all withdrawn subjects (or subjects with missing/partial non-informative SLEDAI-2K data) regardless of treatment failures.”

2.4. Analysis method to Assess the Impact of the Coronavirus Disease 2019 (COVID-19) Pandemic on the Primary Endpoint (RAP Section 7.1.7.1)

The RAP Section 7.1.7.1 states the following text as the first step in the method for the imputation of missing data due to COVID-19:

- A bayesian repeated measures logistic regression model will be fitted to the observed data, using a Markov Chain Monte Carlo (MCMC) approach, adjusting for treatment group, baseline SLEDAI-2K score (≤ 9 vs. ≥ 10), baseline immunosuppressant use (use vs. non-use), and baseline corticosteroid dose (prednisone equivalent ≤ 10 mg/day vs. >10 mg/day). Non-informative priors will be used.

However, the planned approach is not a repeated measures approach, it is an imputation approach that will proceed sequentially through affected visits, so the text ‘repeated measures’ should be removed.

2.5. Clarification on Missing Data for SLEDAI-2K in additional COVID-19 Analyses (RAP Section 7.1.7.4)

Table 3 in the RAP (Section 7.1.7.4) displays a graphical representation of specific scenarios for individual subjects, in terms of their completion status or any Intercurrent Events, and the timing of them in relation to the COVID-19 environment onset date.

In the existing table, there was one row for subjects who complete at Week 52 after the COVID environment onset date. To cover the scenario of missing (or partial non-informative) SLEDAI-2K data, that row has been split into two rows, as shown in [Table 1](#) below:

Table 1 Graphical Representation of the Additional Analyses

| COVID-19 environment Onset date | | Description | Primary Analysis Hybrid | COVID Attributed | COVID Environment | Pre- COVID |
|------------------------------------|--------------|--|-------------------------------|---------------------|----------------------|---------------|
| X | _____0 Comp. | Subject Completes Week 52 on or after COVID-19 environment onset date and has a completed (or partial but informative) S2K Score | R/NR | R/NR | Imputed | Excluded |
| X | _____0 Comp. | Subject Completes Week 52 on or after COVID-19 environment onset date and has a missing or partial non-informative S2K Score that cannot be determined to definitely be either R or NR | NR | Imputed | Imputed | Excluded |

Comp. = Completed; R/NR = Responder/Non-Responder based on SLEDAI-2K criteria; NR = Non-Responder

